3.2 Study Design

Type of study: A multi-centre sensitivity to change study, using the SAQ, other questionnaire measures and clinic data

Duration of the study: 18 months.

Sample size: Between 30 and 50 participants per each of the five participating sites:

1. University Hospitals Plymouth, NHS Foundation Trust, Plymouth, UK
2. Royal Brompton and Harefield NHS Foundation Trust, London, UK
3. University Hospital of South Manchester, Manchester University NHS Foundation Trust, UK
4. Birmingham Heartlands Hospital NHS Foundation Trust, Birmingham, UK
5. Royal Devon and Exeter Hospital NHS Foundation Trust, Exeter, UK

Baseline questionnaire data from participants recruited for this part of the study will be added to the dataset for part 1.

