3.4.3 Sample size calculation

Three types of analysis are planned. Sample size is based on analysis 2 (see below where the sample is divided into quartiles and we test whether there are significant differences between quartiles. Four groups of 25 patients will detect an effect size of 0.3 with a power of 70% at a significance level 5%. The total sample is therefore 100 participants. The addition of a fifth site with the aim of also recruiting 25 patients will mean this analysis remains sufficiently powered even if one of the other sites under-recruits.

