The mean, confidence intervals, and standard deviation of change of the SAQ will be calculated for each level of change in the GRCQ. These means will then be plotted (change in SAQ on x axis, global change on y axis) to show the relationship between change and perceived change at different degrees of change. These results should show that the change in the SAQ increases with increase in global change scores, and will be tested for by analysis of variance. This analysis is needed to show that the MCID is specific to the level of change of 'a little better' or 'a little worse' rather than any other level of global rating of change. The analysis will also check whether 'a little better' is equivalent in terms of 'a little worse' in terms of SAQ change.

Is the MCID transitive – i.e., is the MCID independent of level of deficit of quality of life?

Patients will be allocated to quartiles based on severity of the SAQ score at week 0. The mean, confidence intervals and standard deviation of change scores for change at 'a little better' will be calculated. Analysis of variance will be calculated for the four quartiles to test of transitivity. Effect size (eta) will be calculated. This analysis is needed to show that the MCID level can be applied across the full range of deficit of quality of life.

Are items in the SAQ equivalent with regard to the MCID – i.e., is change in all the 16 SAQ items equivalent in terms of their relationship with the global rating of change?

To test for equivalence, change in each of the 16 items of the SAQ and the SAQ-global will be correlated against the global rating of change score. These correlations will be examined and interpreted. Regression will be explored, but may be ruled out due to co-linearity. This analysis is needed to show whether weighting of items is needed when calculating the MCID, or whether the MCID is based simply on the mean of all items.

Demographic information analyses

In addition, we will also test whether baseline characteristics are similar across the four quartile groups and investigate whether the change in SAQ is related to the collected demographic and clinical data.

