If the above show no problems with the existing methodology, then the MCID will be calculated from the average SAQ change for the rating of 'a little better'. That is, any patient who has provided a global rating of change of 'little better' will contribute an initial and final SAQ score to produce a SAQ difference score for each patient, and the average of the SAQ difference scores across patients will be then form the MCID. If there are problems, then we shall modify the MCID, for example, having different values for different levels of quality of life deficit (see 2 above) or by using a weighting of items (see 3 above).

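### A difference ANOVA across baseline quartiles, powered at 70%, cannot show that one MCID applies at every level of quality-of-life deficit

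*Protocol*

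**What the plan says.** Protocol 3.6, second analysis, divides patients into quartiles of week-0 SAQ score and takes the SAQ change at the global rating *a little better*. Means, confidence intervals, standard deviations and eta are to be calculated. The test is named: "Analysis of variance will be calculated for the four quartiles to test of transitivity". So is its purpose: "This analysis is needed to show that the MCID level can be applied across the full range of deficit of quality of life".

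The end of 3.6 gives the decision: "If the above show no problems with the existing methodology, then the MCID will be calculated from the average SAQ change" at that rating. If problems appear, the MCID may instead take different values at different levels of deficit. The opening of 3.6 makes the same split in terms of checks that come out positive or negative. Neither place says what result counts as a problem.

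Section 3.4.3 bases the sample size on this analysis, in which "we test whether there are significant differences between quartiles". It gives the power statement "Four groups of 25 patients will detect an effect size of 0.3 with a power of 70% at a significance level 5" per cent, and concludes "The total sample is therefore 100 participants". It then mentions "The addition of a fifth site with the aim of also recruiting 25 patients" as protection against under-recruitment elsewhere. Section 3.2 gives another size: "Between 30 and 50 participants per each of the five participating sites".

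**The concern.** The statement to be supported is one of sameness: a single MCID holds from the least to the most impaired quartile. The chosen tool tests for difference. Its 5% error rate limits the chance of wrongly rejecting a common MCID. The error that would harm users of the scale is adopting one threshold when the true value changes with baseline deficit. That error is controlled only through power, which was set at 70%. Fewer patients or noisier scores make a non-significant result, and so the favourable conclusion, more likely.

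Section 1.2 says the MCID is needed for clinical practice, trials and research. If the common value is accepted because the test was weak, one threshold would be used for patients with severe asthma at different levels of quality-of-life deficit who may need different ones.

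**Working it through.** **Inputs.** From 3.4.3: k = 4 groups, n = 25 per group, N = 100, effect size 0.3, alpha 5%, stated power 70%. From 3.4.3 with the fifth site: 100 + 25 = 125. From 3.2: 5 × 30 = 150 to 5 × 50 = 250. Assumptions: the effect size is Cohen's f; 60 is an illustrative number of patients contributing a change at *a little better*; quartiles are of equal size.

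**Step 1: reproduce the stated power.** For a one-way ANOVA, power = P(F′ > F crit), where F′ is non-central F with k − 1 and N − k degrees of freedom and non-centrality N·f². Here the degrees of freedom are 3 and 96, the non-centrality is 100 × 0.3² = 9, and F crit = 2.70. Power is 69.2%, against 70% stated, so the figure reproduces. Other readings fit less well: eta = 0.3 gives 73.7%, eta-squared = 0.3 gives over 99.9%, and a pairwise standardised difference of 0.3 gives 18.4%.

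**Step 2: miss rate at the protocol's own target effect (1 − power, f = 0.3).**

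| N in the ANOVA | Source | Missed |
|---|---|---|
| 60 | assumption | 56% |
| 100 | 3.4.3 | 31% |
| 125 | 3.4.3 with fifth site | 20% |
| 150 | 3.2, lower end | 13% |
| 250 | 3.2, upper end | 1% |

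**Step 3: what f = 0.3 means.** f is the SD of the four group means divided by the within-group SD. Solving for the gap between highest and lowest quartile mean gives 0.60 SD of SAQ change (two quartiles against two), 0.69 (one differs), 0.80 (evenly spaced) or 0.85 (extremes differ, middle two at the midpoint). The target effect is therefore a fairly large gap under any of these patterns.

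**Step 4: illustration with a smaller gap.** The 0.5-SD gap is a benchmark chosen here, not a protocol figure. At N = 100:

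| Pattern of means | f | Missed |
|---|---|---|
| Two against two | 0.250 | 48% |
| One quartile differs | 0.217 | 60% |
| Evenly spaced | 0.186 | 70% |
| Extremes differ, middle two at midpoint | 0.177 | 73% |

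For evenly spaced means the miss rate is 81% at N = 60, 62% at 125, 55% at 150 and 31% at 250.

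**Step 5: what an interval could show.** The half-width of a 90% CI for the difference between two quartile means, in SD units, is t(0.95; N − 4) × √(2/n). At N = 100 this is 1.661 × √(2/25) = 1.661 × 0.283 = 0.47. At N = 250 (n = 62.5) it is 1.651 × √(2/62.5) = 0.30. At N = 60 (n = 15) it is 1.673 × √(2/15) = 0.61. An observed difference of exactly zero fits inside a margin only if the margin exceeds this half-width.

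**The case against.** **The adoption rule is not written as a p-value rule.** A reader might infer that the protocol adopts one MCID whenever the ANOVA is non-significant. It does not say so: 3.6 speaks of positive checks and of an absence of problems, and it also plans confidence intervals and eta for the same check. This stands, and it limits the point. The significance reading is the natural one because 3.4.3 describes the analysis as a significance test and 3.6 attaches no criterion to the other outputs. It remains an inference.

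**A threshold may be left to the SAP.** Fair: the absence of a margin is not in itself the fault. The fault is that the protocol fixes a test, a purpose and a power basis that do not match.

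**The sample may be larger than 100.** Sections 3.2 and 3.4.3 do not agree, and at 250 the target effect is almost never missed. The reverse is also possible, because only patients with a change at *a little better* enter this ANOVA. A larger sample lowers the miss rate but does not turn a difference test into evidence of sameness.

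**The 70% miss rate.** A reader might take a 70% chance of missing a 0.5-SD gap as the size of the problem. That needs evenly spaced means, N = 100 and a benchmark the protocol does not contain. It gives no SD of SAQ change by which to judge whether 0.5 SD matters to patients.

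**Mild against severe patients.** A reader might think the threshold would be shared between mild and severe asthma. All participants have severe asthma (GINA step 4 and 5) and are starting a biologic (3.4.1); the quartiles divide that group by SAQ score.

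**Conclusion.** The point holds in limited form. The named test cannot deliver the stated conclusion, and on the natural reading a failure to find a difference would support one MCID for the whole range. The firm figure is the protocol's own: at 100 patients a difference of the target size is missed about 31% of the time, reading the effect size as Cohen's f. Across the sizes the document allows, the figure falls to 1% at 250; it rises to 56% if only 60 patients contribute. The 0.5-SD results (48% to 73% at N = 100) are illustration only. What the documents do not support is an explicit non-significance rule or a single headline miss rate beyond the planned 30%. The matter should be put right before analysis, and wording is enough to do it.

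**What to change.** In 3.6, state that a non-significant ANOVA will not by itself be taken as showing transitivity. Judge the check on the quartile means and confidence intervals already planned, adding intervals for the differences between quartiles and a margin fixed beforehand in SAQ units. Use all quartile differences: the extreme pair alone, or a slope, can miss a middle quartile that departs from the rest. Name three outcomes:

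- **(a)** All intervals lie inside the margin: claim one MCID for the full range.
- **(b)** Differences are clearly shown: use the option already in 3.6 of different values by level of deficit.
- **(c)** Inconclusive: report the overall MCID with the quartile means and intervals, and state that transitivity was not shown.

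The cost is protocol or SAP wording and agreement on one margin, with no new patients or data. The downside is real: at N = 100 the 90% CI half-width for two quartiles is about 0.47 SD of SAQ change, so with any smaller margin outcome (a) is out of reach, and (c) is a likely result if the quartiles do not clearly differ.

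### Analysis 3 bases item weighting in the MCID on correlations with the change rating, which mix responsiveness with item noise and ignore the size of change in points

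*Protocol*

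**What the plan says.** Protocol section 3.6 plans three checks on the MCID concept before the MCID is fixed. The third asks: "is change in all the 16 SAQ items equivalent in terms of their relationship with the global rating of change". Its test is that "change in each of the 16 items of the SAQ and the SAQ-global will be correlated against the global rating of change score". No criterion is attached: "These correlations will be examined and interpreted". A second method is mentioned conditionally: "Regression will be explored, but may be ruled out due to co-linearity".

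The purpose is explicit: "This analysis is needed to show whether weighting of items is needed when calculating the MCID", the alternative being the simple mean of all items. The closing paragraph of section 3.6 says that, if the checks raise no problem, "the MCID will be calculated from the average SAQ change for the rating of 'a little better". If they do, the MCID may be modified, and one of the two examples given is "by using a weighting of items (see 3 above".

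The same section defines the SAQ score as the unweighted mean of the 16 items. Section 1.1 gives each item a 0-6 scale and describes the global ratings as 0-100. Section 3.3.1 gives the rating of change 11 points, from -5 to 5.

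**The concern.** The quantity to be protected is a number of points. Because the SAQ score is a plain mean of items on one common 0-6 scale, an item's contribution to the MCID is its own mean point change among patients who rate themselves 'a little better'. Items are equivalent for the MCID if those point changes are alike.

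A correlation answers a different question: how closely an item's change follows the rating, relative to that item's total spread. It does not change if a constant is added to every change score or if the item is rescaled. The weighting decision can therefore err in two ways. It can suggest weighting where items move equally but differ in noise, or accept the plain mean where items move by different amounts. Determining the MCID is a stated aim of this part of the study (section 3.1), so a modification made on the wrong evidence would alter a main result.

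**Working it through.** **The plan's own figure.** Analysis 3 has none. The only sizing figure for this part (section 3.4.3: four groups of 25, effect size 0.3, 5% level, 70% power) belongs to analysis 2. It reproduces: a one-way ANOVA with N = 100, four groups and Cohen's f = 0.3 has power 69.2%. Only N = 100 is carried forward here.

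**Inputs.** From the Protocol: 16 items on 0-6, a rating on -5 to 5, N = 100. Assumed, because the documents give no item-level values: the SD of the rating (2 unless stated), each item's slope b in points per rating step, and its residual SD s. 'A little better' is taken as +1.

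**Formula.** If item change = a + b × rating + error, then

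r = b × SD(rating) / √(b² × SD(rating)² + s²).

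The intercept a does not appear, and b and s enter only through their ratio.

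**Equal point change, different noise** (b = 0.30, so b × SD = 0.60):
- s = 0.7: r = 0.60 / √(0.36 + 0.49) = 0.65
- s = 1.8: r = 0.60 / √(0.36 + 3.24) = 0.32

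The items look non-equivalent although each moves 0.30 points per step.

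**Different point change, equal correlation:**
- b = 0.15, s = 0.5: r = 0.30 / √(0.09 + 0.25) = 0.51
- b = 0.30, s = 1.0: r = 0.60 / √(0.36 + 1.00) = 0.51
- b = 0.45, s = 1.5: r = 0.90 / √(0.81 + 2.25) = 0.51

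The items look equivalent although their slopes differ threefold.

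**Level of change.** In a simulated item with rating SD 1.8, b = 0.30 and s = 1.0, adding 0.5 points to every change score moves mean change at +1 from 0.30 to 0.80 and leaves r at 0.473.

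**Sensitivity to the assumed rating SD.** For b = 0.30 with s = 0.6 versus 1.5, r is 0.45 versus 0.20 at a rating SD of 1.0, and 0.78 versus 0.45 at 2.5. For slopes 0.15 and 0.45 with s = 0.5 and 1.5, the two correlations stay equal throughout (0.29 to 0.60).

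**Rounded items bounded at 0-6** (rating SD 1.8). Both patterns persist. Mean changes at +1 of 0.30 and 0.27 go with r = 0.58 and 0.31. Mean changes of 0.15 and 0.40 go with r = 0.38 and 0.43.

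**Similar noise.** With s between 0.9 and 1.3 and b = 0.30, r runs only from 0.60 / √(0.36 + 0.81) = 0.55 to 0.60 / √(0.36 + 1.69) = 0.42.

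**Sampling scatter.** In simulations with N = 100 and 16 items identical in slope (0.30) and residual SD (1.25), with independent residuals, the largest and smallest observed r average about 0.56 and 0.29, a range of 0.27. Residuals correlated across items would narrow this somewhat.

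**The case against.** A reader might infer that a correlation measures only noise and not change. That is too strong. At fixed noise r rises with slope: with rating SD 2 and s = 1.0, slopes of 0.1, 0.3 and 0.6 give r = 0.20, 0.51 and 0.77. If items are about equally noisy, the correlations rank them by responsiveness.

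A reader might also take the full spread of observed correlations as bias from unequal noise. With residual SDs from 0.7 to 1.8, equal slopes and N = 100, that spread averages about 0.67 to 0.22, a width of 0.45. About 0.27 of such a width arises among identical items from sampling alone. Estimated slopes scatter too, but they come with intervals on the scale that matters.

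The protocol frames equivalence as the items' relationship with the rating, and a correlation is a fair description of that. No mechanical rule exists: the correlations are to be interpreted, weighting is only an example of a modification, and nothing says that weights would be computed from the correlations. All this stands and limits the point. What remains is the step from association to weighting a point-scale quantity, which the protocol itself takes.

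Nor do the documents support saying that regression is expected to fail. They say it may be ruled out, and its form is not stated. The collinearity caveat suggests a joint model with all items as predictors of the rating, which would not give each item's change at 'a little better'. Regressing each item's change on the rating, one item at a time, has no such collinearity.

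**Conclusion.** The concern holds in a limited form. The protocol names a statistic for the weighting decision that does not match the MCID it is meant to check, and the decision can err in either direction. The algebra is general; the size is illustrative. Under the assumed values, equal slopes can show r of 0.65 and 0.32, and a threefold difference in slope can show one common r of 0.51. The second case needs noise in proportion to slope, and the first shrinks to 0.55 and 0.42 if residual SDs lie between 0.9 and 1.3.

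These figures show what can happen, not what is likely. A reader might infer that the SAQ items do differ several-fold in change, or that the MCID will be wrong; the documents support neither. The default, an unweighted mean, is unaffected unless the team chooses to weight. The correction is still worth making before the data are analysed, because the MCID is a main aim and a better-matched statistic is readily available.

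**What to change.** In analysis 3, for each of the 16 items on the 0-6 scale, report (a) the mean change at 'a little better' and (b) the slope of item change per rating step. Give both 95% confidence intervals that allow for repeated visits by the same patient. Base the weighting decision on these estimates. This extends to items the means and intervals by rating level that analysis 1 already plans for the SAQ.

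Keep the correlations as supporting description. Keep SAQ-global separate, since its 0-100 scale has other units.

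A repeated-measures model with item, rating and item-by-rating terms is one optional way to obtain the estimates. A non-significant interaction should not be read as proof that the items are equivalent.

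Cost: a few sentences in section 3.6 and a little extra analysis of data already collected.

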3.6 Analysis

The SAQ provides two scores, the SAQ score which is the mean of all 16 domain specific items, and the SAQ-global score which is a single item score based on the SAQ-Global, which itself is based on a Borg scale [21]. Borg scales use multiple quantifiers at empirically derived points along the scale with the aim of achieving a ratio scale. In this analysis plan, the term SAQ will refer to both the SAQ score and the SAQ global score. Separate analyses will be carried out on the SAQ score and SAQ-global. Several analyses will be carried to ensure that the MCID concept is fit for purpose.

Data from 4, 8, 12 and 16 weeks will be compared to the data collected at week 0 (baseline), providing 4 change scores per patient. Patients can indicate any one of 5 levels of improvement in any of the four weeks, or, if there is no change or deterioration, up to 11 types of change. If patients report the same level of global rating of change at each of the four time points (e.g., they record 'a little better' at week 4 and 'a little better at week 8), the average SAQ change score will be calculated for that patient. This average will then be used as the SAQ change for that particular level of global rating of change. This procedure is followed so that each patient can contribute just one value to the population average of the SAQ change score at any level of global change, and which, in the case of the level of 'a little better' is used to calculate the MCID. We shall carry out three analyses to check on the validity of the MCID concept. If the checks come out positive, then the existing method of calculating the MCID (i.e., as the change in the SAQ that maps on to the global rating of change criterion of 'a little better) will be adopted.

If the checks are negative – i.e., suggesting some revision to the way the MCID concept is employed – then we will adapt the methodology in accordance with our findings.

What degree of change on the SAQ is associated with each of the 5 levels of improvement and 5 levels of deterioration on the global rating of change score?

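### Section 3.6 words the MCID input inconsistently, and its analysis of variance across rating levels has no patient effect although one patient can appear at several levels

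*Protocol*

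**What the plan says.** All of this is in Protocol section 3.6.

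- **Change scores.** Weeks 4, 8, 12 and 16 are each compared with week 0, "providing 4 change scores per patient".
- **Averaging rule.** The condition is "If patients report the same level of global rating of change at each of the four time points". The example in brackets has 'a little better' at weeks 4 and 8 only. Of the patient's mean change, the text says "This average will then be used as the SAQ change for that particular level of global rating of change".
- **Purpose of the rule.** The stated aim is this: "each patient can contribute just one value to the population average of the SAQ change score at any level of global change". The same sentence says that the value at 'a little better' is what the MCID uses.
- **First check on the MCID concept.** "The mean, confidence intervals, and standard deviation of change of the SAQ will be calculated for each level of change in the GRCQ". The expected result is that "the change in the SAQ increases with increase in global change scores, and will be tested for by analysis of variance".
- **Closing paragraph.** If the checks raise no problem, "the MCID will be calculated from the average SAQ change for the rating of" 'a little better'. The next sentence explains this: any patient who gave that rating "will contribute an initial and final SAQ score to produce a SAQ difference score for each patient", and these differences are averaged across patients.

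**The concern.** The MCID is a stated aim (section 3.1), so the rule that turns up to four ratings and four change scores into one number per patient should read the same way wherever it is stated. Here the trigger, the example, the purpose and the closing explanation do not all agree. An analyst who applied one sentence in isolation could build a different input from the one intended.

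The second issue is the model. The averaging rule gives one value per patient within a level, but not one value per patient overall. A patient whose rating moves between visits appears at several levels, each time with a change measured from the same week-0 score. An analysis of variance that treats those values as coming from different people has the wrong error term. That analysis is one of the three checks that decide whether the usual MCID method is kept or adapted.

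**Working it through.** **1. The wording, side by side**

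| Element of section 3.6 | When are changes averaged? | Values per patient at 'a little better' |
|---|---|---|
| Trigger | Same rating at all four visits | One if all four agree; otherwise not stated |
| Example | Same rating at weeks 4 and 8 | One |
| Purpose | Whenever a level is repeated | One |
| Closing paragraph, first sentence | Consistent with the purpose | Consistent with the purpose |
| Closing paragraph, explanation | Not mentioned | One initial-to-final difference; rated visit not named |

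The purpose needs averaging at two or more visits. The trigger covers only four out of four.

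Illustration (assumed data, taking +1 as 'a little better'): ratings +1, +1, +3, +4 at weeks 4, 8, 12, 16, with SAQ changes 0.4, 0.6, 1.2, 1.5.

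- By purpose and example, the value at 'a little better' is (0.4 + 0.6)/2 = 0.5.
- By the trigger, the four ratings differ, so the averaging clause does not apply and no rule is given for the 0.4 and 0.6.
- By the closing explanation, with 'final' taken as the last visit so rated, the value is 0.6. One initial and one final score cannot express the average 0.5.

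**2. The analysis of variance across levels**

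Under the purpose rule this patient supplies three values: 0.5 at +1, 1.2 at +3 and 1.5 at +4. With four change scores the maximum is four levels.

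*Correlation between two changes from the same week 0.* With equal SDs, r_0f the correlation of week 0 with follow-up and r_ff that between follow-up visits:

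ρ = (1 + r_ff − 2 r_0f) / (2(1 − r_0f))

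If r_ff = r_0f, ρ = 0.5. If r_0f = 0.5 and r_ff = 0.6, ρ = (1 + 0.6 − 1)/1 = 0.6. These correlations are assumptions; the protocol gives none.

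*Effect on comparing two levels.* Let each level have n values with variance σ², and let a share w of each level's contributors also appear at the other level. Plain analysis of variance takes the variance of the difference in means as 2σ²/n. The true variance is (2σ²/n)(1 − wρ). The true type I error at a nominal 5% is then about P(|Z| > 1.96/√(1 − wρ)). With ρ = 0.6:

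| w | 1 − wρ | 1.96/√(1 − wρ) | True type I error |
|---|---|---|---|
| 0.25 | 0.85 | 2.13 | 3.3% |
| 0.5 | 0.70 | 2.34 | 1.9% |
| 1 | 0.40 | 3.10 | 0.2% |

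*All levels together.* Simulations with ρ = 0.6 and assumed patterns of rating movement gave about 0.3% to 4% at a nominal 5%. A further check used 100 patients, five levels, values averaged within level, no true difference between levels and 3,000 runs per pattern. It gave 0.6% when ratings moved freely between visits and 3.9% when they rarely moved. A model for the visit-level changes with a patient effect (correlation taken as known) gave 4.7% to 5.5% on the same data.

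**3. What is not affected**

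Within one level each patient gives one value under the purpose rule. The per-level means and confidence intervals, including the MCID itself, do not suffer from the repeated patients. The sample size statement in section 3.4.3 is also untouched: four groups of 25 with effect size 0.3 give 69.2% power from the noncentral F distribution, which agrees with the stated 70%.

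**The case against.** The strongest reply is that the intended rule is stated, not merely implied. The purpose clause gives the unit (one value per patient per level) and its use (the MCID). The closing paragraph opens with the same quantity, and its explanation still gives one difference per patient. An analyst would have to apply one phrase and ignore the example beside it. This stands, and it limits the wording point to reconciliation. It also disposes of two stronger inferences:

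- **That 'final' means week 16 whatever the rating there.** Section 3.3.2 does call the 16-week visit the final one, and in the illustration this would give 1.5 instead of 0.5. But the explanation restates a sentence about change for a given rating, so that reading is strained and nothing here rests on it.
- **That repeated ratings enter unaveraged and make the MCID's confidence interval too narrow.** The purpose clause excludes this. Any figure for the narrowing would describe breaking the plan, not following it.

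On the model, the reply is that section 3.6 never says the observations are independent, and that the error structure may be set in an analysis plan not shown here. This stands in part. However, section 2.8 specifies one within and one between factor where a mixed design is meant, while section 3.6 names analysis of variance without qualification for data that its own averaging rule makes repeated within patients.

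A trend test might also be asked for, since change is expected to increase with rating. That is a preference: the same check also aims to show that the MCID is specific to its level, which calls for comparisons between levels.

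**Conclusion.** The point holds in two limited parts.

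1. The operative wording of the MCID input is inconsistent: trigger against example and purpose, and closing explanation against the averaging rule. The intended method can be recovered. No bias in the MCID is shown, and the size of any effect cannot be derived from the protocol.

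2. A plain analysis of variance across rating levels has the wrong error term, because one patient can contribute at up to four levels from one week-0 score. Direction and size depend on the within-patient correlation and on how ratings move between visits. In the assumed cases (correlation 0.6) the test was conservative, with a true type I error of about 0.3% to 4%. A reader might infer that false positives are inflated; the cases examined do not support that. The cost is a check that is harder to pass than its nominal level suggests.

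The two parts together merit a change because they govern a stated aim and the remedy is cheap. Sample size, power and alpha stay as they are.

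**What to change.** - **Averaging rule, section 3.6:** make the condition that the same level is reported at two or more of the four time points.
- **Closing paragraph, section 3.6:** define the difference score as the SAQ at the visit(s) rated 'a little better' minus week 0, averaged within patient by the rule given earlier in the section.
- **First check, section 3.6:** compare rating levels with a model that includes a patient effect, for example a mixed model with a random patient intercept. The per-level means, standard deviations and confidence intervals can stay as planned.

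The cost is two wording edits and slightly more modelling work. No new data are needed, because section 3.5 already collects the SAQ and the global rating together at weeks 4, 8, 12 and 16.
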